12.5 Slit Lamp Biomicroscopy

A slit lamp biomicroscopy examination of the cornea, conjunctiva, anterior chamber, iris, lens, eyelid, and pupil will be performed as per the schedule of assessments. The results will be graded as normal, abnormal NCS, or abnormal CS.

The results will be summarized using numbers and percentages for each treatment arm and for all patients at each visit for each eye (study eye and fellow eye). Percentages will be based on the number of patients in each treatment arm with responses and overall for all patients. Summary table will be presented for normal, abnormal NCS, or abnormal CS in cornea, conjunctiva, anterior chamber, iris, lens, eyelid, and pupil. A patient listing of the slit lamp biomicroscopy parameters will also be produced.

12.6 Intraocular Pressure

Patients' IOP will be assessed in each eye per the schedule of assessments. Results will be taken from a single measurement and will be recorded in millimeters of Mercury (mmHg). For IOP, the mean values and mean change from baseline will be summarized for each eye (study eye and fellow eye) using continuous descriptive statistics by visit for each treatment arm and for all patients. A patient listing of IOP will be produced.

12.7 Dilated Fundoscopy

A dilated fundoscopy examination of the vitreous, retina, macula, optic nerve, and choroid will be performed as per the schedule of assessments. The results will be graded as normal, abnormal NCS, or abnormal CS.

The results will be summarized using numbers and percentages for each treatment arm and for all patients for each eye (study eye and fellow eye). Percentages will be based on the number of patients in each treatment arm with responses. Summary table will be presented for normal, abnormal NCS, or abnormal CS in the vitreous, retina, macula, optic nerve, and choroid. A patient listing of the dilated fundoscopy parameters will also be produced.

CONFIDENTIAL

The contents of this document are confidential to [REDACTED]
Unauthorized use, disclosure, or reproduction is strictly prohibited.

12.8 Physical Examination

Per the eCRF completion guidelines, a complete or brief physical examination will take place per the schedule of assessments. Complete and brief physical exam results for each body system will be graded as normal, abnormal NCS, or abnormal CS. Complete and brief physical exam results will be summarized by treatment arm and for all patients using numbers and percentages at each visit. A patient listing of the physical examination results will also be produced.

12.9 Height, Weight, and BMI

Height (cm), Weight (kg), and body mass index (BMI [kg/m^2]) will be summarized with continuous descriptive statistics for each visit and treatment arm and for all patients. Height will be measured at baseline only. BMI will be calculated at Screening and Baseline. Weight will be measured per the schedule of assessments. Baseline height, weight, and BMI will be summarized on the demographics and baseline characteristics table. Change from baseline for Weight (kg) will be summarized by treatment arm and for all patients. A patient listing of the height, weight, and BMI results will also be produced.

12.10 Vital Signs

Vital signs, including seated pulse rate, systolic and diastolic blood pressure, body temperature, and respiration rate will be summarized with continuous descriptive statistics at each planned data collection visit and time point by treatment arm and for all patients. On dosing days, vital signs will be assessed pre-dose and at 1 and 2 hours (± 15 minutes each) following the start of infusion. Mean vital signs and mean change from baseline will also be summarized to each post-baseline visit and time point. A patient listing of the vital signs results will also be produced.

12.11 Electrocardiogram

Electrocardiograms (ECGs) will be measured in triplicate within a 15-minute period, separated by 1 minute or more. Heart rate (HR), and the PR, RR, QRS, QT, and QTcF (QT interval corrected using Fridericia's formula) intervals will be summarized using continuous descriptive statistics by treatment arm and for all patients at each planned data collection visit and time point. Change from baseline to each post-baseline visit and time point will be also summarized by treatment arm.

A patient listing of the ECG results will be produced. The results for ECG will also be graded as normal, abnormal NCS, or abnormal CS, and these ECG results will be listed only.

CONFIDENTIAL

The contents of this document are confidential to [REDACTED]
Unauthorized use, disclosure, or reproduction is strictly prohibited.

12.12 Clinical Laboratory Data

Clinical laboratory data including hematology, coagulation, serum chemistry, urinalysis, urine drug screen, and additional tests (Follicle-stimulating hormone as applicable, Hepatitis B virus surface antigen, Hepatitis C virus antibody, Human immunodeficiency virus antibody [HIV-1 and HIV-2], severe acute respiratory syndrome coronavirus 2 by polymerase chain reaction (PCR) antibody test, serum or urine pregnancy [for females of childbearing potential only]) are collected at each planned data collection visits.

The quantitative variables will be summarized by treatment arm with continuous descriptive statistics. Change from baseline will also be summarized by treatment arm and for all patients. Categorical results will not be summarized. Listings will be produced including an additional listing for abnormal values only.

13. Pharmacokinetic Analyses

PK will be assessed using the PK Population. placebo patients will not be assessed for PK. Where the data allow, noncompartmental analyses (NCA) will be used to estimate Day 1 serum PK parameters for LASN01 after single and repeat IV dosing. Final analyses will be performed after the database lock and will use actual sampling times. The effect of antidrug antibodies (ADA) on LASN01 exposure will be assessed. A PK report will be generated summarizing the results.

13.1 Summary of Concentration Versus Time Data

LASN01 concentration data will be summarized by study treatment arm (LASN01 300 mg, LASN01 600 mg, [REDACTED]) and nominal time using descriptive statistics. Linear and semi-logarithmic plots of the individual patient Day 1 LASN01 serum concentrations versus actual time data will be generated. Additionally, a comparison of the treatment arms (low versus high dose) will be shown graphically using linear and semi-logarithmic plots of the arithmetic mean (with SD) serum concentrations versus nominal time data. A patient listing of all serum LASN01 concentrations will be provided.

CONFIDENTIAL

The contents of this document are confidential to [REDACTED]
Unauthorized use, disclosure, or reproduction is strictly prohibited.

Individual and arithmetic mean (with SD) LASN01 concentrations from the predose samples obtained throughout the study will be plotted versus Study Day.

13.2 LASN01 Pharmacokinetics

Where the data allow, LASN01 serum concentration versus time data will be subjected to NCA. Individual patient serum concentration versus time data will be downloaded into validated [REDACTED] [REDACTED] for PK analyses. Actual sample collection times relative to the time of dosing will be used for the final PK calculations (actual sampling time for predose samples will be set to zero).

Where appropriate, the following LASN01 serum parameters will be generated:

C_{max}	Maximal concentration
C_{min}	Minimal concentration (i.e., predose trough concentration; For Day 1, this value will be obtained from the Day 29 predose sample)
T_{max}	Time at which the maximal concentration is observed
T_{last}	Time point with the last measurable concentration
AUC_{0-28d}	Area under the concentration time curve from time 0 to 28 days post-dose; calculated using the linear up/log down trapezoidal rule
AUC_{0-inf}	Area under the concentration time curve from time 0 extrapolated to time infinity; calculated as $AUC_{0-last} + (C_{last} / \lambda_z)$ where C_{last} is the predicted concentration at T_{last}
AUC_{0-last}	Area under the concentration time curve from time 0 to the time point with the last measurable concentration; calculated using the linear up/log down trapezoidal rule
λ_z	Terminal elimination rate constant; estimated by linear regression of the log concentration versus time curve
$t_{1/2}$	Terminal half-life; calculated as $\ln(2)/\lambda_z$, where λ_z is the terminal elimination rate constant
CL	Clearance; calculated as $dose/AUC_{0-inf}$
V_{ss}	Steady-state volume of distribution; calculated as MRT_{0-inf}/CL where MRT_{0-inf} is the mean residence time extrapolated to time infinity

CONFIDENTIAL

The contents of this document are confidential to [REDACTED]
Unauthorized use, disclosure, or reproduction is strictly prohibited.

V_z Volume of distribution based on the terminal phase; calculated as $\text{dose}/(\lambda_z \times \text{AUC}_{0-\text{inf}})$

Three measurable time points must be available in the concentration versus time profile for AUC values to be reported. Parameters based on the terminal phase of the concentration versus time data will only be reported if the following acceptance criteria are met: there are a minimum of 3 time points with measurable LASN01 concentrations in the terminal phase of the PK profile (not including C_{max}), $R^2 > 0.9$, and the percent of $\text{AUC}_{0-\infty}$ extrapolated from the last measurable concentration to time infinity ($\text{AUC}_{\% \text{extrap}} < 20\%$). Uniform data weights will be selected as part of the regression step options.

Predose values trough (C_{min}) and end of infusion values over the course of the study will be evaluated for accumulation compared to the trough value after the Day 1 dose.

A patient listing of PK parameters will be provided. Individual concentration values for PK parameters may be excluded from the calculation of descriptive statistics and graphical displays, e.g., due to a deviation of actual versus planned sampling time, dosing error, dosing holiday, or obvious outlier. Any excluded data, however, will be listed along with the reason for exclusion.

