2.2.2.2. Nonclinical Safety Pharmacology

[REDACTED]

[REDACTED]

[REDACTED]

2.2.2.2.1. *Nonclinical Toxicology*

[REDACTED]

[REDACTED]

[REDACTED]

[REDACTED]

2.2.2.2.2. *Immunogenicity*

[REDACTED]

2.2.2.2.3. *Genotoxicity*

No genotoxicity studies are required since LASN01 is a monoclonal antibody.

2.2.2.2.4. *Reproductive Toxicity*

No reproductive toxicity studies have been conducted to date.

2.2.2.3. *Clinical Summary*

A first-in-human 4-part Phase 1/2a (LASN01-CL-1101) randomized, double-blind placebo-controlled, SAD, and MAD clinical study is ongoing in Australia to determine the safety, tolerability, preliminary efficacy, immunogenicity, and PK properties of LASN01 in healthy volunteers and in patients with pulmonary fibrosis or TED, as well as preliminary efficacy biomarkers in patients with TED.

In the healthy volunteer portions of the study (ie, SAD and MAD cohorts), interim, topline, unblinded safety and PK data for 58 healthy volunteers are available (data cutoff date of 02JUN2023). In the completed SAD portion of the study (Part A), LASN01 doses of 25, 100, 300, 600, and 1200 mg IV were evaluated. In the completed MAD portion of the study (Part B), LASN01 doses of 600 (B1) and 1200 (B2) mg IV were evaluated. The study is ongoing with planned multiple doses of 1200 mg in patients with IPF and PF-ILD (Part C) and TED (Part D).

Overall, 35 healthy volunteers (60.3%) experienced 61 TEAEs. A total of 13 healthy volunteers (22.4%) experienced 18 TEAEs considered potentially related to study drug (LASN01 or placebo) by the Investigator. There were no serious or severe TEAEs reported and no subject withdrew from the study due to a TEAE. The incidence of TEAEs was not dose related. Most TEAEs were not related to study drug and all were mild or moderate in severity.

The PK of LASN01 follows approximately dose-proportional PK based on both the SAD and MAD cohorts. The mean half-life estimates ranged from 165 to 335 hours at doses ≥ 25 mg/day administered as a single IV dose or as 2 administrations 14 days apart, supporting the extended dosing intervals under consideration for clinical studies. The PK profile in healthy volunteers is consistent with that observed in the cynomolgus monkey.

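### Two PK rules in SAP 13.2 are wrong as written: Vss is MRT divided by CL, and end-of-infusion accumulation is judged against a trough

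*SAP*

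**What the plan says.** SAP 13.2 lists the noncompartmental parameters with their formulas. The Vss line reads "Steady-state volume of distribution; calculated as MRT_{0-inf}/CL", where MRT0-inf is the mean residence time. In the same list CL is dose divided by AUC0-inf, and Vz is dose divided by the product of λz and AUC0-inf. Protocol 9.2.6 names Vss but gives no formula, and SAP 1 says that the SAP's methods replace the protocol's.

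On accumulation, SAP 13.2 treats predose troughs in the same way as the post-infusion samples: "end of infusion values over the course of the study will be evaluated for accumulation compared to the trough value". The trough meant is the one that follows the first dose, which the Cmin line identifies: "For Day 1, this value will be obtained from the Day 29 predose sample". Protocol 1.3 (schedule footnote on PK samples) places post-infusion samples on Days 1 and 337 only.

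On acceptance, SAP 13.2 states: "Parameters based on the terminal phase of the concentration versus time data will only be reported if the following acceptance criteria are met". The criteria are at least three terminal points besides Cmax, R² above 0.9, and less than 20% of AUC0-inf extrapolated. SAP 13 names Day 1 parameters as the target of the analysis, and the Day 1 profile ends at the Day 29 predose sample. For scale, Protocol 2.2.2.3 reports from Phase 1: "The mean half-life estimates ranged from 165 to 335 hours".

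**The concern.** A volume of distribution has to come out in litres, and the Vss line does not. An accumulation ratio has to compare like with like, and a post-infusion value set against a trough is large even if the drug does not accumulate at all. A programmer or PK analyst who followed either line literally would report a wrong quantity, and no other text in the two documents corrects it.

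The extrapolation limit raises a different question. It is a standard check on AUC0-inf. Here it also decides whether λz and half-life are reported, so whether a patient's half-life enters the summary depends partly on how long that half-life is.

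**Working it through.** The plan gives no figure of its own on these points, so there is nothing to reproduce first.

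**Inputs from the documents:** the formulas and criteria above; a dosing interval of 28 days = 672 h; Phase 1 mean half-lives of 165 to 335 h. **Assumed, not in the documents:** linear one-compartment kinetics; CL of 0.005 to 0.02 L/h; between-patient CV of half-life 20–30%. Infusion time is neglected (60 mL at 200 mL/h is 0.3 h).

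**1. Vss.**
- Units as written: h ÷ (L/h) = h²/L.
- From the SAP's own lines, Vz = dose/(λz × AUC0-inf) = CL/λz. With one compartment, MRT = 1/λz and Vss = Vz, so Vss = CL × MRT.
- MRT = half-life/ln 2, which is 238.0 h at 165 h and 483.3 h at 335 h.
- At CL = 0.01 L/h, CL × MRT = 2.38 L and 4.83 L. MRT/CL gives 23,804 and 48,330 h²/L.
- In these units the two differ by 1/CL², or 2,500 to 40,000 for CL of 0.02 to 0.005 L/h.

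**2. End of infusion against the Day 1 trough.** Let f = 2^(−672/half-life), the fraction left after one interval. With no accumulation the comparison gives 1/f. True steady-state accumulation is 1/(1 − f). The comparison at steady state gives 1/[f(1 − f)].

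| Half-life | f | No accumulation | Steady state, as written | True accumulation |
|---|---|---|---|---|
| 165 h | 5.9% | 16.8 | 17.9 | 1.06 |
| 250 h | 15.5% | 6.4 | 7.6 | 1.18 |
| 335 h | 24.9% | 4.0 | 5.3 | 1.33 |

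The as-written value falls down the column while true accumulation rises. Comparing troughs with the Day 29 predose trough, or Day 337 end of infusion with Day 1 end of infusion, returns 1/(1 − f).

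**3. Extrapolation limit.** In the same model, the extrapolated share at Day 29 is f. It reaches 20% at a half-life of 672/log2(5) = 289 h.
- The Day 29 visit window of ±3 days puts the sample 25 to 31 days after dosing and moves the cutoff to 258–320 h.
- If 10–20% of AUC comes from a distribution phase, the cutoff is 310–336 h.

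For lognormal half-lives cut at 289 h:

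| True mean half-life | Excluded (CV 20–30%) | Mean among those kept |
|---|---|---|
| 165 h | 0.2–2% | 162–165 h |
| 250 h | 20–26% | 215–231 h |
| 335 h | 64–74% | 240–258 h |

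**The case against.** The Vss line could be a text-extraction fault. That is unlikely, because the neighbouring Vz line keeps its multiplication sign. A better argument is that SAP 13.2 sends the data to validated PK software, which would probably compute Vss correctly whatever the SAP says. That stands: the certain harm is to the written specification, and a reader should not infer that the reported Vss will be meaningless.

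The accumulation sentence may be loose drafting. It defines no ratio, so the documents do not show that accumulation will be reported several-fold too high. They do name the wrong comparator for end-of-infusion values. Early termination (SAP 1), patients who did not reconsent, and a range of 7 to 13 doses (SAP 3.1) also mean that Day 337 values may be few.

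On the extrapolation limit, a reader might infer a third error, with half-life biased low and clearance biased high. The documents do not support that. The limit is a conventional reliability criterion, and applying it to half-life is defensible when the terminal points are Days 8, 15 and 29. The Phase 1 range covers means across doses from 25 mg upward, with no value given for 300 or 600 mg, so the effect could be negligible or severe. A long half-life can also reflect a large volume as well as slow clearance, so the direction for CL does not follow from the half-life cutoff alone.

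The consequence is limited too. The secondary PK endpoint is serum concentration at specified times, which none of these rules changes. Of the four dose-proportionality parameters in SAP 13.3, only AUC0-inf is subject to the limit.

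**Conclusion.** Two rules need correcting. The Vss formula is dimensionally wrong and contradicts the CL and Vz formulas beside it; this rests on no assumption. The end-of-infusion comparison is wrong as literally worded. Its size (4.0 to 16.8 with no accumulation, and 5.3 to 17.9 at steady state against a true 1.33 to 1.06) rests on a one-compartment model over the protocol's half-life range. The trough comparison in the same sentence is sound.

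The extrapolation limit is a conditional suggestion only. Exclusion depends on half-life, with a cutoff near 289 h (258–336 h by sampling time and distribution phase). At an assumed CV of 20–30% it removes from about 0–2% of patients at a mean of 165 h to 64–74% at 335 h. Where this trial falls in that range cannot be told from the documents.

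All of this bears on secondary PK reporting and not on the primary efficacy result.

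**What to change.** In SAP 13.2:

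1. Replace the Vss formula with Vss = CL × MRT0-inf.
2. Split the accumulation sentence: compare later troughs with the Day 29 predose trough, and Day 337 end of infusion with Day 1 end of infusion in patients who have both. State the number of pairs.
3. As a suggestion, keep the 20% limit, report how many profiles it excludes in each dose arm, and show λz and half-life with and without the profiles it flags. The three-point and R² criteria stay as they are.

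The cost is SAP wording and a few extra table rows. The samples are already in the schedule.

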13.3 Statistical Assessment of Dose-Proportionality

Dose proportionality of study drug will be assessed for parameters C_{max} , $\text{AUC}_{0-\text{last}}$, $\text{AUC}_{0-28\text{d}}$, and $\text{AUC}_{0-\text{inf}}$, using the power model:

$$\ln(\text{Parameter}) = \beta_0 + \beta_1 \times \ln(\text{Dose})$$

Dose proportionality will be evaluated by estimating the slope (β_1) along with its 90% CI. The power model will be fit by restricted maximum likelihood (REML) using [REDACTED] with both the intercept and slope terms as fixed effects. The predefined dose proportionality criterion over the dose range will be met if the 90% CI for β_1 is within 0.8 to 1.25. Dose proportionality will only be checked between the LASN01 600 mg and LASN01 300 mg treatment arms.

14. Pharmacodynamic Analyses

The Pharmacodynamic Population will be used to summarize counts and percentages of patients with positive and negative responses of ADA for LASN01 300 mg, LASN01 600 mg, [REDACTED] at each visit. Percentages will be based on the number of patients in each treatment arm with responses at the visit. A table and a listing will be presented.

CONFIDENTIAL

The contents of this document are confidential to [REDACTED]
Unauthorized use, disclosure, or reproduction is strictly prohibited.

15. Interim Analyses

An interim analysis was completed when approximately 50% of evaluable patients enrolled in the randomized treatment arms completed at least 8 weeks in the study. The interim analysis contained both masked and unmasked outputs for the Sponsor's review. Unmasked outputs were prepared by designated unmasked personnel not otherwise involved in study conduct to avoid operational bias. As this is an early phase proof-of-concept study where control over the type-1 error rate is not required, the alpha remained at 0.1.

Masked IA outputs included a Treatment-Naïve Active group (consisting of all the randomized treatment naive patients), [REDACTED], and an All Patients arm. Since masked table summaries had a different column structure, masked tables were added to the IA for patient dispositions, demographic and baseline characteristics, and TEAEs by SOC and PT. Efficacy output for the IA had the same column structure for both Masked and Unmasked outputs.

16. Changes from Protocol-Stated Analyses

The following changes from protocol-stated analyses are made to the SAP by the sponsor:

Due to several consent withdrawals and patients declining to re-consent for the 12-month extension, the Sponsor unmasked the clinical team to assess whether early study termination was appropriate. Investigators, the CRO clinical operations team, and CRO statisticians remained masked until the database lock. The following specific changes have been made and the additions are considered exploratory:

- Due to early termination of the study, only proptosis measured by Hertel and Total CAS will be analyzed in tables. Other secondary and exploratory endpoints will be listed.
- Either eye responder analyses have been added for proptosis by Hertel and Total CAS, and either eye continuous analyses have been added for Total CAS. Either eye responder and continuous Total CAS analyses will identify an eye at Week 37 (Day 253) and use that same eye in the analysis for each visit.
- A sensitivity analysis, as defined in protocol Section 9.2.4, has been added for Total CAS in the study eye and separately for either eye. Only the pooled active group will be compared to placebo. The sensitivity analysis of the primary responder rate for proptosis from protocol Section 9.4.2. has been removed.

CONFIDENTIAL

The contents of this document are confidential to [REDACTED]
Unauthorized use, disclosure, or reproduction is strictly prohibited.

- An ANCOVA model has been added to existing mean and mean change from baseline Total CAS tables. The model includes baseline and treatment as factors and will be run separately for each eye (study eye and either eye) and visit. Only the pooled active group will be compared to placebo.
- 95% CI for proptosis responder analysis has been removed
- LOCF has been added as the imputation method for missing data for all efficacy analyses.
- Per Protocol Population analyses have been removed.
- ODO analyses have been added for all proptosis and CAS tables to check robustness of results.

17. References

1. Giner G, Smyth GK (2016). statmod: probability calculations for the inverse Gaussian distribution. R Journal 8(1), 339-351.
2. ICH Harmonised Tripartite Guideline: Statistical Principles for Clinical Trials E9. International Council for Harmonisation of Technical Requirements for Pharmaceuticals for Human Use. 05 February 1998.

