3.1 General Study Design

This proof-of-concept Phase 2 study comprises the randomized, double-masked, placebo-controlled treatment arms in patients with TED with no prior anti-IGF-1R treatment [REDACTED]

[figure not shown]
The randomized treatment arms will be used to evaluate the efficacy, safety, tolerability, PK, immunogenicity, and PD properties of 2 dose levels (300 and 600 mg) of LASN01 administered IV Q4W 7 to 13 doses in anti-IGF-1R-naïve patients with TED. [REDACTED]

The general study design for treatment-naïve patients is depicted in Figure 1 for the European protocol version 7.1 and the randomized treatment-naïve patients in the United States protocol version 7.0.

CONFIDENTIAL

The contents of this document are confidential to [REDACTED]
Unauthorized use, disclosure, or reproduction is strictly prohibited.

Figure 1. General Study Design for Treatment-Naïve Patients

Following 49 weeks of dosing (last dose administered on Day 337), patients will be followed for an additional 24 weeks for a total study duration of 73 weeks (End of Study [EOS] visit on Day 505 ±7 days).

Study participation (Baseline to the EOS visit) will require approximately 505 days, not including the Screening period. The Screening visit will occur up to 30 days before Day 1.

Treatment assignments will be performed centrally by [REDACTED]

A Safety Review Committee (SRC) will be formed to periodically review safety and available PK and PD data. For the randomized, double-masked treatment arms, the SRC will examine masked data. The first data review will occur after at least six patients have been treated and followed for six weeks. Subsequent meetings may take place every 12 months, depending on enrollment rates and SRC discussions. The SRC Charter outlines the committee's structure and provides further conduct details. A separate SRC shell will be created to document and confirm SRC outputs.

Interim analysis (IA) may be performed when at least 50% of evaluable patients in the randomized treatment arms complete at least 8 weeks in the study. [REDACTED] The IA will include both masked and unmasked outputs for Sponsor review. A separate unmasked statistician

CONFIDENTIAL

The contents of this document are confidential to [REDACTED]
Unauthorized use, disclosure, or reproduction is strictly prohibited.

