3.2.1 STUDY TREATMENTS

This study will include approximately 36 evaluable patients with TED in 4 treatment arms. Treatment-naïve patients will be randomized (in a 1:1:1 ratio) upon enrollment to LASN01 in either a high-dose (600 mg Q4W ×7-13 doses) or low-dose (300 mg Q4W ×7-13 doses) treatment arm or to placebo. [REDACTED]

[REDACTED] Treatment arms for the randomized and open-label patients are shown in Table 1. The protocol was amended as additional safety data became available to increase the duration of treatment with LASN01.

CONFIDENTIAL

The contents of this document are confidential to [REDACTED]
Unauthorized use, disclosure, or reproduction is strictly prohibited.

Table 1. Multiple Dose Study Design

Randomized Treatment Arm	Dose	Number of Doses	Number of Patients
1	Low-dose LASN01 (300 mg Q4W)	13	8
2	High-dose LASN01 (600 mg Q4W)	13	8
3	Placebo (Q4W)	13	8
Total Number of Patients			24

4. Sample Size

This study will enroll up to 36 evaluable patients with TED across four treatment arms. Approximately 24 patients will be randomized in a 1:1:1 ratio to receive LASN01 600 mg Q4W, LASN01 300 mg Q4W, or placebo.

Randomized Treatment Arms:

- The pooled primary analysis represents a 2:1 randomization of pooled LASN01 (300 mg and 600 mg arms) to placebo with about 24 patients.
- The placebo response rate is assumed to be ~15% (based on Teprotumumab FDA approval data from 2020).
- Assuming a pooled LASN01 response rate of 65% (an absolute treatment effect of 50% over placebo), a sample size of 8 patients per arm provides approximately 81% power at a 10% significance level using a one-sided Fisher's exact test.
- If the placebo response rate is 10%, the power increases to approximately 90% at the same significance level.
- Power calculations were performed using R Version 4.2.1 (R Core Team, 2022), employing simulation methods with 10,000 iterations implemented via the 'statmod' package (Giner, 2016).

CONFIDENTIAL

The contents of this document are confidential to [REDACTED]
Unauthorized use, disclosure, or reproduction is strictly prohibited.

5. Analysis Populations

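### SAP 13.3 puts unscaled 0.8 to 1.25 limits on the power-model slope over a 2-fold dose range, a criterion that proportional PK would seldom meet with 8 patients per arm if between-patient CV is about 20% or more

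*SAP*

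**What the plan says.** Protocol 9.2.6 promises a statistical assessment of dose proportionality and leaves the details to the SAP. SAP 13.3 supplies them. It fits ln(Parameter) = β0 + β1 × ln(Dose) to Cmax, AUC0-last, AUC0-28d and AUC0-inf, "with both the intercept and slope terms as fixed effects". The slope is to be estimated "along with its 90% CI", and the predefined criterion is met if that interval "is within 0.8 to 1.25. Dose proportionality will only be checked between the LASN01 600 mg and LASN01 300 mg treatment arms".

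The doses therefore differ by a factor of two. SAP 3.1 describes "2 dose levels (300 and 600 mg) of LASN01", and SAP Table 1 plans 8 patients in each arm. That number comes from the primary responder test: SAP Section 4 states that "a sample size of 8 patients per arm provides approximately 81% power at a 10% significance level". Neither document gives a between-patient CV, a reason for the slope limits or the chance of meeting them. SAP 13.3 says when the criterion is met and does not say what a failure would mean.

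On earlier data, Protocol 2.2.2.3 (Clinical Summary) says: "The PK of LASN01 follows approximately dose-proportional PK based on both the SAD and MAD cohorts".

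**The concern.** The numbers 0.8 and 1.25 are familiar as limits for a ratio of geometric means. A power-model slope is an exponent, and the exposure ratio that a given slope implies depends on the dose range. Over a range as narrow as 2-fold, unscaled slope limits are tighter than the ratio limits they resemble. A narrow range also makes the slope imprecise, because ln(2) divides the standard error. The two effects compound when there are only 8 patients per arm.

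At stake is how the PK report reads. It could carry up to four lines saying that a predefined criterion was not met, next to earlier data described as approximately proportional, when the trial had little chance of meeting it. The SAP gives no guidance on reading such a result.

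**Working it through.** **The plan's own figure.** The only power stated in the documents is for the primary endpoint. Exact enumeration of the one-sided Fisher test (16 vs 8 patients, 65% vs 15% responders, alpha 0.10) gives 0.818, against about 81% stated. With 10% on placebo it gives 0.897, against about 90%. Both reproduce. This is the source of 8 per arm; nothing comparable is stated for SAP 13.3.

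**What the limits mean.** The dose ratio is r = 600/300 = 2, and ln 2 = 0.693. The dose-normalised exposure ratio implied by slope β1 is r^(β1 − 1).

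- Slope 0.80: 2^(−0.20) = 0.871
- Slope 1.25: 2^(0.25) = 1.189

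For a ratio of 0.80 to 1.25, the slope limits are:

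- 1 + ln(0.80)/ln 2 = 0.678
- 1 + ln(1.25)/ln 2 = 1.322

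The SAP window is 1.25 − 0.80 = 0.45 wide, against 1.322 − 0.678 = 0.644. It allows 0.20 below 1 and 0.25 above. This step needs no assumption.

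**Precision with 8 per arm.** With two doses, β1 is the difference in mean log exposure divided by ln 2. Dose varies between patients, so:

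- σ = sqrt(ln(1 + CV²))
- SE(β1) = σ × sqrt(1/8 + 1/8) / ln 2 = 0.721σ
- t(0.95, 14 df) = 1.761, so the 90% CI half-width is about 1.27σ

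The interval fits inside a 0.45-wide window only if 1.27σ ≤ 0.225, that is, if the observed CV is at most about 17.8%. At CV 20%, σ = 0.198 and the half-width is 0.252, already more than the room on either side of 1.

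**Failure rate when the true slope is exactly 1.** These are one minus the pass rates from 400,000 simulated trials, 8 per arm. The CV is an assumption, varied because the documents give none.

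| CV | Half-width | Fails 0.80 to 1.25 | Fails 0.678 to 1.322 |
|---|---|---|---|
| 10% | 0.127 | 21% | 1% |
| 15% | 0.190 | 72% | 23% |
| 20% | 0.252 | 95% | 61% |
| 25% | 0.313 | 99.3% | 86% |
| 30% | 0.373 | 99.9% | 96% |

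**What those failures look like.** When the slope is 1, a 90% CI excludes 1 in only 10% of trials. At CV 20%, at least 95% − 10% = 85% of all trials would therefore fail with an interval that includes 1. Such failures show imprecision, not departure from proportionality.

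**Eight is a ceiling.** The PK Population (SAP 5.3) requires a complete dose and a valid parameter. SAP 13.2 reports AUC values only with three measurable points, and terminal-phase parameters only with R² above 0.9 and less than 20% extrapolated. With 6 per arm, the SAP limits pass 60%, 14% and 2% of the time at CV 10%, 15% and 20%.

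**Size needed.** For an 80% chance of passing at CV 20%, 25% and 30%, the SAP limits need 30, 46 and 65 patients per arm. The scaled limits need 15, 22 and 31.

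**The case against.** The strongest reply has four parts.

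First, nothing is miscalculated. The SAP predefines a margin on the slope, and a sponsor may choose a strict one. Neither document says that the limits must match a 0.80 to 1.25 ratio. This stands in part: the fault is an unexplained margin that the design can rarely satisfy at moderate variability, not a wrong sum.

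Second, a reader might infer that the rule fails almost always, whatever the truth. The documents do not support that. They give no CV, and at 10% proportional PK would pass 79% of the time. The statement needs a CV of about 20% or more.

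Third, a reader might infer that the SAP would declare LASN01 non-proportional, or that any failure would be due to the limits alone. SAP 13.3 draws no conclusion from failure. Nor are the limits the only cause: the scaled ones still fail 61% to 96% of the time at CV 20% to 30%. Sample size and dose range matter at least as much there.

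Fourth, little depends on the result. The secondary PK endpoint is serum concentration, no dose decision in either document rests on this test, and the study ended early. SAP 13.3 already estimates the slope with its CI. All of this stands and limits the importance of the point. It does not make the pass/fail rule informative.

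**Conclusion.** The point holds in a conditional form. It is certain, from algebra, that the SAP limits require a dose-normalised ratio of 0.871 to 1.189, which is tighter than 0.80 to 1.25. How much that matters depends on variability. With 8 per arm and exactly proportional PK, the criterion is usable at CV 10%, doubtful at 15% and close to unattainable from 20%. These rates assume log-normal exposure, equal variance in the two arms and full retention of 8 per arm; losing patients makes them worse.

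Two causes act together: limits not scaled to the dose range, and few patients over a 2-fold range. Rescaling helps most at CV 15% to 20% and does not rescue the test at 25% or above. Importance is modest, since the analysis is secondary PK and leaves efficacy and safety conclusions untouched.

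**What to change.** Change the criterion sentence in SAP 13.3 so that the estimate is the result. For example: *The slope β1 and its 90% CI will be reported for each parameter, together with the equivalent 600:300 dose-normalised ratio, 2^(β1 − 1), and its 90% CI. No met/not-met conclusion will be drawn.* The ratio adds no information with two doses, but it is easier to read.

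If a criterion has to stay, set the slope limits to 0.68 to 1.32, derived for the 2-fold range. Add that a 90% CI extending beyond the limits but including 1 is inconclusive and is not evidence of non-proportionality.

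The cost is one edited sentence, with no new data or patients. The downside is that the PK report gives up, or softens, a formal pass/fail statement. Under the fallback, the sponsor should still expect an inconclusive result more often than not if CV is about 20% or more.
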